### **Preliminary results Fitforlife pilot study**

During 2015-2016, 99 participants were included. A majority were males (60 persons) and the mean age was 28.2 years. The study was originally designed as a waiting list study but due to

problems with the open care units this turned out to be impossible. Of the 99 persons 39 did not attend any sessions, the rest attended between 1-52 sessions, mean 13.1(SD 12.1). Trailmaking A test time (visual attention) improved 8.5 seconds (SD 20.4) in those that attended >1 session and 5.4 (SD 6.5) in those that did not attend. Trailmaking B, (visual attention and task shifting), improved 10.4 seconds (SD 42.8) in attenders versus 4.6 (SD 31.7) in non-attenders.

Camberwell assessment of need showed that at the initial examination 33 persons reported difficulties with social contacts while at the end of the intervention 17 of those reported no problems. Likewise, 24 persons reported problems with close relations at baseline while 11 of them reported no problem at the end. In the proposed study this will be measured in a more extensive way. During an open house for participants and relatives there were reports about improvement in daily life such as "started to care about his looks", "cleans his room". During spring 2017 the cognitive tests will be analysed and linked with inflammatory markers. The study has given us experience on how to organise exercise for persons with psychosis. After the first wave four participants were educated as peer mentors. At least one peer-mentor was present in all sessions in wave two and three. The peer mentors were responsible for organizing parts of the sessions under supervision of educated trainers. Since the study finished the mentors have worked as peer mentor trainers, offering sessions to patients at an open care unit for FEP. The staff promote the sessions during their meetings with their patients and discussion about physical activity levels is a part of all patients' individual care programme.

**Study objectives:** See separate information

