### **Statistical analysis plan**

Baseline descriptions will be presented and used in the different analyses to see if gender, duration of psychosis, neuroleptics affects the different outcomes.

The main outcome social function will be analyzed using  $\chi^2$  tests and analysis of variance for categorical outcomes using data from baseline to 6 months. Pre- to post-intervention (within-group) analyses will be performed using paired-sample *t*tests, with effect sizes (Hedges' *g*) calculated for statistically significant values. The participants will be divided according to attended number of training sessions. This will be done in quartiles and used to look at between group differences (analysis of covariance- ANCOVA). A sub analysis will be done including those with accelerometer data from the entire study period. Baseline score will be included as covariates in each model.

Parametric test assumptions will be checked before running all analyses. Normality will be assessed using the Shapiro–Wilks test and normal probability plot, and homogeneity of variance using Levene's test. For analyses involving unequal sample sizes, Welch's test might be considered. Similar procedures will be used when analyzing blood samples, inflammatory and metabolic markers as well as cognitive test data. Normative data from the cog state data base will be used for comparison. Multilevel analysis will be used taking into account the included open care units.

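### Hedges' g is planned only for statistically significant, uncontrolled pre-post tests, and no effect estimate or interval is specified for the attendance comparison

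*SAP*

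**What the plan says.** The second paragraph of the SAP plans within-group tests of change: "Pre- to post-intervention (within-group) analyses will be performed using paired-sample" *t*-tests. Hedges' g is attached to these tests and is to be "calculated for statistically significant values". No standard deviation is named as the standardiser.

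The same paragraph then groups participants by number of sessions attended: "This will be done in quartiles and used to look at between group differences", by ANCOVA with the baseline score as covariate. No effect size, adjusted mean difference or confidence interval is named for that analysis. Hedges' g appears nowhere else in either document.

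The third paragraph carries the approach to the other outcomes: "Similar procedures will be used when analyzing blood samples, inflammatory and metabolic markers as well as cognitive test data". I read this as including the effect-size rule. It also mentions Cogstate normative data and a multilevel analysis for care units.

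The Protocol (Methodology; Strengths and limitations) describes a non-randomised open trial, explains why it was not randomised, and describes no control arm.

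**The concern.** Two things are at stake.

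**The significance condition.** An outcome whose paired test is not significant gets no effect size, so readers cannot tell a precise null from an imprecise one. Outcomes that pass are a selected set, and when the true change is small that selection pushes the average reported g upward.

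**Where the effect size is attached.** A pre-post change in an uncontrolled cohort mixes any exercise effect with practice, time and regression to the mean. The comparison nearer the trial's question is the one by attendance, and that is the one with no specified estimate or interval.

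**Working it through.** The plan states no effect-size figure to reproduce. The checks below use the pilot (Protocol, Preliminary results Fitforlife pilot study).

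**Inputs**
- Trail Making A improvement: attenders 8.5 s (SD 20.4), non-attenders 5.4 s (SD 6.5).
- Trail Making B: "improved 10.4 seconds (SD 42.8) in attenders versus 4.6 (SD 31.7) in non-attenders".
- Attendance: "Of the 99 persons 39 did not attend any sessions", leaving 60 with at least one session.
- Recruitment target: 300 (Protocol, Methodology). I also use 150, as if half had paired data.

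**Assumptions, none stated in the documents**
- Two-sided alpha is 0.05.
- The pilot SDs are SDs of change.
- All 60 and 39 were retested. These are upper bounds, since numbers retested are not given and the pilot's attender figures are described as being for more than one session.
- g is standardised by the SD of change.

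**Step 1. Smallest g that can be reported.** g_min = t(0.975, n-1)/√n × J, with J = 1 - 3/(4(n-1) - 1).
- n = 300: 1.968/17.32 × 0.9975 = 0.113.
- n = 150: 1.976/12.25 × 0.9950 = 0.161.

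**Step 2. Pilot change in the whole cohort.** The paired tests are not restricted to non-attenders, so both groups are combined.
- B mean: (60×10.4 + 39×4.6)/99 = 8.1 s.
- B SD: √{[59×42.8² + 38×31.7² + (60×39/99)×5.8²]/98} = 38.7. Standardised change 8.1/38.7 = 0.21.
- A by the same formulas: mean 7.3 s, SD 16.4, standardised change 0.44.

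**Step 3. Effect of the filter.** Paired t-tests were simulated (1,000,000 draws per setting), keeping g only when p < 0.05. The last two columns are mean reported g divided by true g.

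| True standardised change | Power, 300 / 150 pairs | Ratio, 300 pairs | Ratio, 150 pairs |
|---|---|---|---|
| 0.21 (B, pooled) | 0.95 / 0.72 | 1.03 | 1.18 |
| 0.145 (B, non-attenders: 4.6/31.7) | 0.71 / 0.42 | about 1.2 | about 1.5 |
| 0.44 (A, pooled) | 1.00 / 1.00 | 1.00 | 1.00 |

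At 150 pairs the power of 0.72 for the pooled B change means g would go unreported about 28% of the time. Reported without the condition, g averages to the true value.

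**Step 4. Within-group g by attendance, Trail Making A.** g = (mean/SD) × J.
- Attenders, n = 60: 8.5/20.4 × 0.987 = 0.41 (t = 3.23, p = 0.002).
- Non-attenders, n = 39: 5.4/6.5 × 0.980 = 0.81 (t = 5.19, p < 0.001).

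With fewer retested, the non-attenders' change stays significant down to 9 people (g 0.75), while the attenders' change loses significance at 24 or fewer. The ordering of the two g values comes from the SDs. On one common SD (pooled within groups, 16.4) they are 8.5/16.4 = 0.52 and 5.4/16.4 = 0.33, before correction, and the order reverses. So the unnamed standardiser matters.

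Trail Making B in non-attenders does not show the same thing: g 0.14, p = 0.37 at n = 39.

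**Step 5. The between-group difference.** Welch SE = √(s₁²/n₁ + s₀²/n₀), at 60 versus 39.
- A: 8.5 - 5.4 = 3.1 s; SE √(6.94 + 1.08) = 2.83; 95% CI -2.5 to 8.7.
- B: 10.4 - 4.6 = 5.8 s; SE √(30.5 + 25.8) = 7.50; 95% CI -9.1 to 20.7.
- At 30 versus 20 retested: A -5.0 to 11.2; B -15.4 to 27.0.

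All four intervals include zero.

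**The case against.** The strongest reply is that the SAP already contains what is needed. It plans a between-group ANCOVA with baseline adjustment, a multilevel model for units and a comparison with norms, and the Protocol discloses the lack of randomisation. Any ANCOVA yields adjusted group differences. That stands: the gap is that no measure or interval is pre-specified, not that none could be reported. None of those analyses removes the significance condition on g.

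A reader might infer that the filter roughly doubles effect sizes. The documents do not support that as a general statement. A ratio near 2 (1.95 at 150 pairs) needs the whole cohort to change like pilot non-attenders on Trail Making B, with that change divided by the attenders' SD (4.6/42.8 = 0.107). No pilot group has that combination. With the pooled pilot data the filter hardly matters at 300 pairs.

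A reader might also infer that the SAP will present paired tests as proof that exercise works. It never says so. It also does not label them descriptive.

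It is fair, too, that the two-group Welch intervals above are not the planned quartile ANCOVA: they lack baseline adjustment and ignore clustering. They show why a between-group interval is needed and do not predict its width. All the figures concern Trail Making, because the pilot gives no attender/non-attender split for social function, the main outcome.

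**Conclusion.** The point holds as a defect in what is specified. Followed literally, the SAP gives no effect size for non-significant outcomes, overstates small changes that pass the filter, and leaves the attendance comparison without a stated estimate or interval.

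The certain harm is selective reporting. The inflation is secondary: negligible once the true standardised change is about 0.2 or more at 300 pairs, and material only for smaller changes or fewer pairs. The pilot's Trail Making A result shows separately that within-group g can rank non-attenders above attenders, so it cannot stand in for an exercise effect. The sizes rest on the assumed alpha, on the SDs being of change, and on the retest numbers. For social function the size is unknown.

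Reporting the attendance contrast would not make it causal, because participants choose how often to attend.

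**What to change.** 1. Replace the significance condition with: 'Hedges' g with 95% CI will be reported for every continuous outcome regardless of significance.' Name the standardiser in the same sentence.
2. Pre-specify one attendance contrast, for example the highest versus the lowest attendance group. Report its baseline-adjusted difference with 95% CI from the planned ANCOVA/multilevel model. Present it as the between-group result, alongside the pre-post changes, which are descriptive. A difference on the outcome's own scale is enough; g is optional here.

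The cost is SAP wording and a few more table columns, with no new data. The estimates will look less favourable and less precise, and the attendance contrast stays confounded by self-selection, which the report should say.

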## **Methodology**

Study design: Non randomized open trial.

*Study population:* Patients affected by psychosis at open care psychiatric units who are responsible for taking care of psychosis in Sweden.

*Sample size:* Our aim is to recruit 300 patients including mentors at each unit.

*Variables list including data collection tools:*

1. From the medical records: age, gender, diagnosis, time of first contact with psychiatry, medication
  - App questions on overall function using WHODAS 2.0
  - App question on social network: qualitative and quantitative
  - App questions: smoking, alcohol consumption and illicit drug use
  - Cognitive tests: Cogstate (performed at a computer) and Trail making A and B
  - Submaximal fitness test: Åstrand
  - Physical activity pattern, including sedentary time, low-intensity physical activity and exercise, assessed by a simple accelerometer on a subsample.
  - Body measurements: length, weight, hip-waist measure, blood pressure.
  - Blood samples: Blood lipids, HBA1C, TNFalfa, CRP, Il-6

*Plan of analyses:* See separate information

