## **Intervention including time plan**

A team consisting of one of the mentors from Fitforlife, a health pedagogic, and one or two from the research group will come to each included open care unit.

Day 1; Upstart meeting led by a research group member.

Day 1-4; Education of the new mentors led by the health pedagogic assisted by mentor(s) from Fitforlife pilot study.

Day 1-5; Baseline examinations (see above for data collection tools) of all the potential participants by the local contact person(s).

Day 5-14; Start of the training. Initially supported by the health pedagogic and the mentor(s) from Fitforlife pilot study.

Day 14-70: Training sessions led by the local mentors. Supported by phone and online by the health pedagogics and the mentors from Fitforlife. During this time 1-3 visit(s) from the health pedagogic to each mentor during a training session.

Day 70-75: Follow up assessments by the local contact person.

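### The pre-post paired t-tests use only people with a follow-up value, so they may overstate the change in all recruited patients if non-attenders return less and improve less; the planned multilevel analysis would not correct this

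*SAP*

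**What the plan says.** The SAP (Statistical analysis plan) states: "Pre- to post-intervention (within-group) analyses will be performed using paired-sample" t-tests, with Hedges' g for significant results. It names no analysis population, no method for missing follow-up and no expected loss.

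Attendance enters in one place: "The participants will be divided according to attended number of training sessions", in quartiles, for a baseline-adjusted ANCOVA. That analysis also needs a follow-up value. Clustering is covered by one sentence: "Multilevel analysis will be used taking into account the included open care units".

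The Protocol (Methodology) describes a "Non randomized open trial" and describes no control arm. Under Intervention including time plan, baseline examinations fall on Days 1-5, before training starts, and are made "of all the potential participants by the local contact person(s". Follow-up is at Day 70-75, whereas the SAP analyses the main outcome, social function, up to six months. The section on measurements during the intervention has local coordinators record compliance.

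The pilot section reports: "Of the 99 persons 39 did not attend any sessions". Trail Making A "improved 8.5 seconds (SD 20.4) in those that attended >1 session and 5.4 (SD 6.5) in those that did not attend". For Trail Making B the improvements were 10.4 s (SD 42.8) and 4.6 s (SD 31.7).

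**The concern.** The people measured at baseline will include some who never train, because baseline comes first and the pilot had many such people. A paired test keeps only those who return. If return depends on attendance, and attendance goes with improvement, the within-group mean describes those who stayed. With no control arm described, no comparison group exists in which similar losses might offset this.

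A reader might also take the multilevel analysis to deal with missing values, since likelihood models are often used that way. That works only if missingness can be explained by what is in the model. As described, the model contains the care units and the baseline score, but has no stated role for attendance in handling missing follow-up.

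**Working it through.** **No plan figure to reproduce.** The sample size is a recruitment aim ("Our aim is to recruit 300 patients including mentors at each unit") with no power, effect size or dropout allowance.

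**Inputs from the Protocol's pilot section.** Attender share pa = 60/99 = 0.606; non-attender share pn = 39/99 = 0.394. Mean improvement in attenders (a) and non-attenders (n): test A 8.5 and 5.4 s; test B 10.4 and 4.6 s. The pilot means contrast more than one session with none, so the 60/39 split is approximate.

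**Assumed inputs.** The follow-up shares r1 (attenders) and r0 (non-attenders) are in neither document, so a range is shown.

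**Step 1, full-cohort change** = pa·a + pn·n.
- A: (60×8.5 + 39×5.4)/99 = 7.28 s
- B: (60×10.4 + 39×4.6)/99 = 8.12 s

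**Step 2, completer mean** = (60·r1·a + 39·r0·n)/(60·r1 + 39·r0). For B at 90%/50%: (54×10.4 + 19.5×4.6)/(54 + 19.5) = 651.3/73.5 = 8.86 s.

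| Follow-up, attenders / non-attenders (assumed) | A, s (vs 7.28) | B, s (vs 8.12) |
|---|---|---|
| 90% / 90% | 7.28 (0%) | 8.12 (0%) |
| 90% / 70% | 7.46 (+2.5%) | 8.45 (+4.2%) |
| 90% / 50% | 7.68 (+5.5%) | 8.86 (+9.2%) |
| 90% / 30% | 7.95 (+9.2%) | 9.37 (+15.4%) |
| any / 0% | 8.50 (+16.8%) | 10.40 (+28.2%) |
| 70% / 90% | 7.09 (−2.6%) | 7.76 (−4.4%) |

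**Step 3, what sets the direction.** Bias = (a − n) × (attender share among completers − pa). For B at 90%/50%: 5.8 × (54/73.5 − 60/99) = 5.8 × 0.129 = 0.75 s. The bias is zero if either factor is zero, and it reverses if one factor changes sign.

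**Step 4, how firm is a − n?** If all 60 and 39 were assessed, SE = √(SDa²/60 + SDn²/39).
- A: √(20.4²/60 + 6.5²/39) = 2.83, so 3.1 s (95% CI −2.5 to 8.7)
- B: √(42.8²/60 + 31.7²/39) = 7.50, so 5.8 s (95% CI −8.9 to 20.5)

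Both intervals include zero.

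**Step 5, would a mixed model repair it?** The simulation used 300 people, 4,000 runs and the pilot test B means and SDs, with missingness depending on attendance only. Mean improvement in seconds:

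| Follow-up | All enrolled | Paired completers | Two-time likelihood model, no attendance | Same, with attendance, averaged over all enrolled |
|---|---|---|---|---|
| 90% / 50% | 8.12 | 8.90 | 8.90 | 8.13 |
| 90% / 30% | 8.07 | 9.31 | 9.30 | 8.05 |

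With attendance correlated 0.3 with baseline, at 90%/30%, the model without attendance still gives 9.34 s against 8.10 s. A random-intercept model fitted once to 20,000 simulated people gave 9.47 s against 8.12 s. These simulations had no unit level. A unit effect can absorb differences in attendance between units, but not selective return within a unit.

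**The case against.** The strongest objection is that a conditional risk could be read as an established bias. A reader might infer that the paired test does overstate improvement and that the error favours the intervention. The documents do not support that. They give no follow-up rate by attendance. The pilot reports change in non-attenders, so at least some were reassessed, and the Protocol does not restrict the Day 70-75 assessment to attenders. The pilot contrast is imprecise, and Trail Making is not the main outcome. The new trial also runs training inside each unit with local mentors, so 39% non-attendance may not recur. All of this stands, and it is why the direction is conditional here.

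A reader might also infer a fixed size. Changes of 0.4 and 0.1 SD with 85%/40% follow-up give (0.61×0.85×0.4 + 0.39×0.40×0.1)/(0.61×0.85 + 0.39×0.40) = 0.331 SD against 0.61×0.4 + 0.39×0.1 = 0.283 SD, which is 17% too large. None of those four inputs is in the documents. The same follow-up with the pilot means gives 517.74/66.6 = 7.77 s (A, +7%) and 602.16/66.6 = 9.04 s (B, +11%).

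Three further points are fair in part:
- The SAP does not offer the multilevel analysis as a missing-data remedy. That is true; the point is only that it should not be taken for one.
- The attendance-quartile ANCOVA is largely protected if missingness depends only on attendance. It does not repair the overall mean change.
- The SAP names no target population and assigns the main outcome to chi-square tests and analysis of variance, so the paired change is not declared the headline result. The bias here is relative to everyone with a baseline, and the SAP should say whether that is its target.

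**Conclusion.** The concern holds in conditional form. It is certain that the paired test excludes people without follow-up, that no missing-data method is given, and that recorded attendance is not used for this purpose. Whether the result is an overstatement depends on non-attenders both returning less and improving less. The second condition has support in direction only; the first is not addressed in the documents.

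On the pilot means, with 90% of attenders followed, the overstatement runs from 0% at equal follow-up through 5.5% (A) and 9% (B), then 9% and 15%, to a ceiling of 17% and 28%. The ceiling needs no non-attender to be followed, which did not happen in the pilot. These limits apply to this route only; loss that also depended on improvement among attenders could add to them. A likelihood model without attendance removes essentially none of the bias. One with attendance removes it, provided missingness is random within attendance groups.

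This should be corrected in the SAP, but it does not invalidate the study.

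**What to change.** - Name the analysis population as all participants with a baseline.
- Replace the completer-only paired t-test with multiple imputation that includes sessions attended, baseline score and unit. Alternatively, use a likelihood model with attendance, averaged over the attendance distribution of all enrolled.
- State that the follow-up assessment is sought regardless of attendance, and report follow-up by sessions attended.
- Add one delta-adjusted sensitivity analysis in which missing patients are assumed not to improve. This is deliberately pessimistic, since pilot non-attenders did improve.
- Reconcile the SAP's six-month horizon with the Protocol's Day 70-75 assessment, because the time point determines the dropout.

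The cost is SAP wording, modest analysis work and the effort of following non-attenders; attendance is already recorded. The reported improvement may be smaller. The change does not separate an intervention effect from practice effects or regression to the mean, which would need a comparison group.

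### Hedges' g is planned only for statistically significant pre-to-post changes, so non-significant outcomes get none and the reported values are selected on their result

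*SAP*

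**What the plan says.** The SAP (section Statistical analysis plan, the paragraph on the main outcome) states: "Pre- to post-intervention (within-group) analyses will be performed using paired-sample" t-tests. It then says that Hedges' g will be "calculated for statistically significant values". This is an explicit rule, and no other place in the protocol or SAP plans g for results that are not significant. No significance level is given.

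The next paragraph describes the checks of test assumptions and then adds: "Similar procedures will be used when analyzing blood samples, inflammatory and metabolic markers as well as cognitive test data". That plausibly carries the rule over to the laboratory and cognitive outcomes. Because the sentence follows the assumption checks, it may refer only to those.

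The chi-square, analysis of variance, attendance-quartile ANCOVA and multilevel analyses carry no such filter and are not at issue here.

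**The concern.** Whether an effect size is reported depends on the result it is meant to describe. Two things follow.

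- **Missing values.** An outcome that misses significance gets no planned g, whatever the power. A small change estimated precisely and a possibly important change estimated poorly then look the same to the reader. The protocol's outcomes are on many different scales (disability, cognition, fitness, lipids, inflammatory markers), which is where a standardised measure helps most.
- **Selection bias.** Only estimates large enough to cross the significance threshold are shown. Their average lies further from zero than the true effect, markedly when power is low and negligibly when it is high.

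A reader comparing outcomes would therefore see an incomplete set of effect sizes, possibly inflated.

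**Working it through.** The plan states no power, alpha, target effect or dropout, so there is no figure of its own to reproduce.

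**Inputs**
- Number of pairs: the protocol's Methodology section says "Our aim is to recruit 300 patients including mentors at each unit". This is read as 300 in total. If it means 300 per unit, the inflation is smaller. The values 200 and 100 below are bare assumptions. The value 75 is 300/4, the number per test if within-group means within each attendance quartile.
- Alpha: two-sided 0.05, assumed.
- Standardiser: the SD of the change scores, assumed.
- Pilot changes (protocol, Preliminary results Fitforlife pilot study): Trail Making A "improved 8.5 seconds (SD 20.4) in those that attended >1 session and 5.4 (SD 6.5) in those that did not attend"; Trail Making B "improved 10.4 seconds (SD 42.8) in attenders versus 4.6 (SD 31.7) in non-attenders". The printed SDs are assumed to be SDs of change.
- Pooling weights: "Of the 99 persons 39 did not attend any sessions", which gives 99 − 39 = 60 against 39. This assumes that all 99 were retested; the pilot section gives no number tested and defines attenders for the tests as more than one session.

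**Pooled pilot effects**

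Mean = (60·m₁ + 39·m₂)/99. SD² = [59·s₁² + 38·s₂² + (60·39/99)·(m₁ − m₂)²]/98.
- A: mean (510 + 210.6)/99 = 7.28; SD = √[(24553.4 + 1605.5 + 227.1)/98] = 16.41; ratio 0.444.
- B: mean (624 + 179.4)/99 = 8.12; SD = √[(108078.6 + 38185.8 + 795.1)/98] = 38.74; ratio 0.209. Equal weights give about 0.20.

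**Smallest reportable value**

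|g| must exceed J·t(0.975, n−1)/√n, where J is the Hedges small-sample correction. This is 0.113 for 300 pairs, 0.139 for 200, 0.197 for 100 and 0.228 for 75.

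**Average g when it is reported**

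With true standardised change d, t = (Z + d√n)/√(χ²(n−1)/(n−1)) and g = J·t/√n. The mean of g was taken over simulated results with |t| > t(0.975, n−1), using 4,000,000 draws per setting (1,000,000 for 75 pairs). Power is from the noncentral t distribution, and the chance of no g is 1 − power.

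| Pairs | True d | Power | No g | Mean reported g | Inflation |
|---|---|---|---|---|---|
| 300 | 0.10 (assumed) | 0.408 | 59% | 0.155 | +55% |
| 300 | 0.15 (assumed) | 0.736 | 26% | 0.176 | +17% |
| 300 | 0.20 (assumed) | 0.932 | 7% | 0.208 | +4% |
| 300 | 0.209 (pilot B) | 0.951 | 5% | 0.216 | +3% |
| 300 | 0.30 (assumed) | 0.999 | 0.1% | 0.300 | +0.1% |
| 300 | 0.444 (pilot A) | 1.000 | 0% | 0.444 | 0% |
| 200 | 0.20 (assumed) | 0.804 | 20% | 0.225 | +12% |
| 200 | 0.209 (pilot B) | 0.839 | 16% | 0.230 | +10% |
| 100 | 0.20 (assumed) | 0.508 | 49% | 0.279 | +40% |
| 100 | 0.209 (pilot B) | 0.546 | 45% | 0.283 | +35% |
| 75 | 0.20 (assumed) | 0.401 | 60% | 0.312 | +56% |

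A true 0.444 stays within 0.5% at both 200 and 100 pairs. Without the filter, mean g equals the true value in every setting; for example, 0.200 for a true 0.20.

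**The case against.** The strongest reply is that little turns on this. In the only setting tied to the documents' own numbers, pilot values with 300 pairs, the inflation is 0 to 3% and g is missing at most 5% of the time. The larger percentages rest on assumed effects or assumed numbers of pairs. The pilot anchor is itself soft: the number tested is unknown, and the two Trail Making A SDs differ threefold. It also illustrates cognitive outcomes, to which the rule extends only plausibly; for social function, the main outcome, no standardised pilot effect is given. Mean changes are not barred, g can be recovered from t and n, and an unfiltered g from an uncontrolled comparison would still mix the intervention's effect with practice and time.

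Most of this is fair, and it limits the weight of the point without removing it. The SAP does not plan to print t and n for non-significant results, so recovery is not assured. The target of 300 is a recruitment aim with no dropout allowance, and high power for social function cannot be assumed. The 0 to 3% figure also holds only if the cohort is analysed as one group; the per-quartile reading makes the bias larger. The missing g does not depend on the amount of inflation.

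**Conclusion.** The concern holds. It is a reporting fault that is cheap to correct, not a threat to the inference. The certain part is that non-significant paired comparisons have no planned g. The inflation is conditional: negligible for true effects of about 0.30 or more with 300 pairs, and material for effects of about 0.15 or less, or for effects near 0.20 if the analysed pairs fall to around 200 or below. These sizes rest on the assumed two-sided 0.05, the SD-of-change scale and a total of 300 pairs, and should be read as illustrations. Whether the rule reaches the blood, metabolic and cognitive outcomes is likely but not certain.

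**What to change.** Replace the clause with wording such as:

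> Mean change and Hedges' g (standardised by the SD of the change scores, or another stated standardiser), each with a 95% confidence interval, will be reported for every pre- to post-intervention outcome analysed by paired t-test, regardless of statistical significance.

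The defect itself needs only the significance condition removed and the standardiser named. The confidence intervals are a recommended addition, so that a small g can be judged for precision. The sponsor should also say whether the clause applies to the laboratory and cognitive outcomes.

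The cost is one SAP clause, a standardiser chosen in advance and longer results tables. The change removes the selection bias. It does not remove the confounding in an uncontrolled pre-post comparison.

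### Welch's test is offered for unequal group sizes rather than unequal variances, Levene's test leads to no action, and Welch's test cannot carry the baseline covariate in the planned ANCOVA

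*SAP*

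**What the plan says.** The relevant text is in the SAP, under Statistical analysis plan.

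- **Groups and model.** Participants are divided by number of sessions attended: "This will be done in quartiles and used to look at between group differences", by ANCOVA, with the baseline score as a covariate in each model.
- **Checks.** "Parametric test assumptions will be checked before running all analyses". The SAP then names Shapiro–Wilk for normality and, for "homogeneity of variance using", Levene's test. It does not say what happens if Levene's test rejects.
- **Remedy.** "For analyses involving unequal sample sizes", Welch's "test might be considered". No other remedy for unequal variances is named.
- **Reach.** "Similar procedures will be used when analyzing blood samples, inflammatory and metabolic markers as well as cognitive test data". Trail Making A and B are among the cognitive tests in the Protocol's Methodology section.
- **Clustering.** A multilevel analysis is to take the care units into account.

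The Protocol's section on the pilot results supplies the only evidence on spread by attendance: "Trailmaking A test time (visual attention) improved 8.5 seconds (SD 20.4) in those that attended >1 session and 5.4 (SD 6.5" in those who did not attend. For Trail Making B the change SDs are 42.8 and 31.7. The same section says that 39 of 99 participants attended no session.

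**The concern.** The condition and the remedy do not match. Unequal group sizes alone do not disturb the F test when variances are equal. Unequal variances can disturb it, most of all when sizes differ as well. The SAP measures variances but does nothing with the result, and attaches its one remedy to sizes.

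The remedy also does not fit the model. Welch's test compares unadjusted group means, while the planned between-group analysis adjusts for baseline. An analyst who wanted to apply the clause would have to drop the covariate or improvise another method after seeing the data.

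At stake is the false-positive rate of the attendance comparison. A dose-response reading of session numbers could rest on an F test that rejects more often than its nominal level.

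**Working it through.** The documents give no alpha, power or sample-size derivation on this point, so there is no figure of the plan's to reproduce.

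**Inputs**
- From the Protocol, pilot results: change SDs for Trail Making A 6.5 (non-attenders) and 20.4 (attenders); for Trail Making B 31.7 and 42.8; 39 of 99 with no session.
- From the Protocol, Methodology: a target of 300, taken here as the total.
- Assumed: two-sided alpha 0.05; normal errors; the attender SD in every group above the zero-session group.

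**Step 1: variance ratios.** Trail Making A: 20.4²/6.5² = 416.16/42.25 = 9.85. Trail Making B: 42.8²/31.7² = 1831.84/1004.89 = 1.82.

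**Step 2: group sizes.** 39/99 = 39.4%, and 300 × 39/99 ≈ 118 with no session. More than a quarter are tied at zero, so the 25th percentile is 0 and all 118 fall in the lowest group. The second group holds the remainder up to the median, 150 − 118 = 32. The upper two hold 75 each, apart from further ties. Result: about 118/32/75/75.

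**Step 3: why the F test moves.** With equal means, the expected between-group mean square is Σ(1 − nᵢ/N)σᵢ²/(k − 1), and the expected residual mean square is Σ(nᵢ − 1)σᵢ²/(N − k). The F test is centred properly only if these agree.

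- *Trail Making A, 118/32/75/75.* Between: (0.6067 × 42.25 + 0.8933 × 416.16 + 2 × 0.75 × 416.16)/3 = 340.5. Residual: (117 × 42.25 + 179 × 416.16)/296 = 268.4. Ratio 1.27.
- *Trail Making B, same sizes.* Between: (0.6067 × 1004.89 + 0.8933 × 1831.84 + 1.5 × 1831.84)/3 = 1664.6. Residual: (117 × 1004.89 + 179 × 1831.84)/296 = 1505.0. Ratio 1.11.
- *Trail Making A, four groups of 75.* Both are (42.25 + 3 × 416.16)/4 = 322.7. Ratio 1.00.

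The inflation arises because the largest group has the smallest variance and pulls the pooled error down.

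**Step 4: real alpha.** Simulated ANCOVA, equal adjusted means, one baseline covariate, 20,000 runs per cell, no clustering:

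| Group sizes | SD pattern | Classical F | HC3 |
|---|---|---|---|
| 118/32/75/75 | Trail Making A | 11.0% | 5.2% |
| 118/32/75/75 | Trail Making B | 7.1% | 5.1% |
| 118/32/75/75 | equal | 4.8% | 5.0% |
| 117/61/61/61 | Trail Making A | 10.8% | 5.2% |
| 75 × 4 | Trail Making A | 6.0% | 5.1% |
| 75 × 4 | Trail Making B | 5.0% | 4.8% |

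The 117/61/61/61 row covers the alternative of dividing the remaining participants evenly. Without the covariate, the classical F test gives 11.0% and 7.0% in the first two rows, and Welch's ANOVA stays between 4.8% and 5.2% in every configuration tried. The third row shows that unequal size alone calls for no correction.

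If two or three of four equal groups had the low SD, the unadjusted F test would run at 7.0% or 8.1%. The pilot gives no reason to expect the low SD beyond the non-attenders.

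**The case against.** The clause can be read charitably. The sentence before it plans a variance check, and unequal sizes are where unequal variances harm the F test most, so offering Welch there is not senseless. The wording is permissive and does not exclude Welch elsewhere. This softens the criticism but does not remove it: no step connects the variance check to any action, and the test named cannot hold the covariate.

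The case against a large effect is stronger, and several readings that go further should be set aside.

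- **That quartile groups are near equal, so the size condition would never be met.** At the pilot's 39% non-attendance the groups would be clearly unequal and the condition would be met. With four equal groups the inflation is small in any case.
- **That pilot variances differ almost tenfold in general.** This holds for Trail Making A only; for Trail Making B the ratio is 1.8.
- **That the main outcome is affected to this degree.** The main outcome is social function. The documents give no SDs for it by attendance, and the SAP assigns it χ² tests and analysis of variance without ranking the quartile ANCOVA as the main comparison.
- **That pairwise quartile contrasts would be wrong in both directions.** The SAP specifies no pairwise contrasts.

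It is also fair to say that the pilot SDs describe raw change in attenders and non-attenders, not baseline-adjusted residuals by quartile. The group sizes behind them are not reported, and the attender SD is labelled as for more than one session, while 60 people attended at least one.

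**Conclusion.** The point holds in a limited form. The SAP's rule is aimed at the wrong condition, is optional, and does not fit the planned model; its variance check has no consequence. If attendance and spread resemble the pilot, the classical ANCOVA F test has a real alpha of about 10 to 11% for an outcome behaving like Trail Making A and about 7% for one like Trail Making B. With equal group sizes it is about 5 to 6%.

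These figures rest on 300 as the total, the pilot rate of zero attendance, an assumed alpha of 5%, normal errors, and one common SD in all groups above zero attendance. They concern secondary cognitive outcomes and say nothing measured about social function. This is a worthwhile improvement rather than a threat to the trial's main conclusion.

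**What to change.** Replace the sample-size condition. Use unequal-variance methods by default for all between-group comparisons:

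- Welch's test for unadjusted comparisons.
- For the baseline-adjusted comparison, either group-specific residual variances in the multilevel model already planned, or HC3 standard errors, in a cluster-aware form wherever care unit is accounted for. Plain HC3 does not deal with clustering. The number of units is not stated; if it is small, the multilevel option is the safer of the two, because cluster-robust standard errors are unreliable with few clusters.

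Levene's test can stay as a description, but should not decide the method: a default avoids choosing the test after looking at the data. Add one sentence on how participants with no sessions enter the quartiles, since that largely determines the group sizes.

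The cost is SAP wording. When variances are equal, HC3 held 5.0% at 118/32/75/75, so there is no type I penalty, only a very small loss of efficiency.
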